1.0 Study Summary

Title:	Stratification of Clinically Vulnerable People for COVID-19 Risk Using Antibody Testing (STRAVINSKY)
Funding Body	NIHR- National Institute for Health and Care Research
Rationale:	Although the COVID-19 vaccination program has proved extraordinarily successful, clinically vulnerable (CV) patients remain at risk of SARS-CoV-2 infection, severe COVID-19 and death. Large (inter)national studies have previously identified patient groups who generate sub-optimal immune responses to COVID-19 vaccines, and those at highest risk of severe COVID-19. Although the precise immune correlates of protection against severe COVID-19 are not defined and this may be different in different patient groups. Recent emerging data in patient groups suggest that the serological response to vaccination is a critical determinant in COVID-19 outcomes. In this study we will i) perform a retrospective meta-analysis using previous studies to enhance stratification of patient groups for clinical risk and ii) assess if SARS-CoV-2 serological responses to COVID-19 vaccines can be used to risk stratify CV people for COVID-19 clinical outcomes.
Aim & Objectives:	Primary objectives: a) To define and assess the predictive value of SARS-CoV-2 spike serology measurements for COVID-19 clinical outcomes (infection rates and disease severity) in CV people. Secondary objectives: a) To evaluate the serological vaccine responses (magnitude and durability) of CV patients to bivalent or other vaccines given during the study period 2023 onwards b) To assess the functional activity of anti-spike IgG antibodies against new SARS-CoV-2 variants in CV patients during the study period 2023 onwards c) To perform a detailed retrospective analysis using pre-existing data from large national studies that may further inform the patient groups that will be enrolled in the prospective study. Exploratory objectives: a) To evaluate alternate methods to predict COVID-19 infection/hospitalisation should antibody testing fail to predict relevant clinical outcomes (e.g. QCOVID4 score and T cell responses). b) To understand whether the serology vaccine response, in those with suboptimal responses to primary course, can be further enhanced with increasing doses of vaccination.

Study Design:

The STRAVINSKY study encompasses a multicentre prospective, observational cohort study involving multiple sites within the UK, in addition to retrospective analysis of data previously acquired in national studies.

In the prospective study a large number of patients will be recruited from prespecified clinical groups and enrolled through online/remote consent procedure. Blood samples will be acquired by the volunteer and sent to a central laboratory for serology testing. A subgroup of patients will be recruited and donate blood in a face-to-face visit for more detailed immune analysis. Clinical data, alongside vaccine history and COVID-19 infection outcomes will be recorded at each visit. Volunteers are expected to attend for up to four visits over 2023-2024.

The retrospective analysis will use pre-existing data from large national studies that may further inform the patient groups that will be enrolled in the prospective study.

Number of participants in the prospective study:

Up to 3000 individuals will be recruited including:

Remote cohort: 2600 will be recruited and remotely sampled.

In-person cohort: 400 individuals will be recruited and attend an in-person appointment for in-depth sampling from selected hospitals (Birmingham, Oxford, Southampton, and Imperial).

Eligibility criteria for the prospective study:

Inclusion criteria

Participants will meet ALL the following:

- The individual meets the diagnostic or treatment criteria set out in **TABLE 2**, page 13.
- 18 years or older.
- The individual must have capacity to provide written informed consent or in cases where this is not possible, a legal representative who is able to make an informed decision on their behalf.

Exclusion criteria

Participants will meet NONE of the following:

- Does not have a legal representative who is able to make an informed decision about consent to the study.
- Individuals will be excluded if they have received any monoclonal antibody therapy against SARS-CoV-2 within the 26 weeks prior to the first study blood sampling (either as a treatment for infection or pre-exposure prophylaxis). Recipients of regular immunoglobulin therapy are eligible*.
- Age less than 18 years.

Sample collection for the prospective study:

Remote cohort: Capillary blood sampling by dried blood spot.

In-person cohort: Up to 60 ml of blood to assess blood antibody levels, T cell responses and store samples for exploratory studies; Saliva and nasal samples.

All patients will be given a COVID-19 swab kit at home to return to the investigators when they test positive for COVID-19 infection.

2.0 Background

COVID-19 vaccines are the main strategy employed by governments globally to protect their populations against SARS-CoV-2 infection. However, the protection conferred by these vaccines is not equivalent for everyone. Individuals with immunosuppression, either because of underlying disease or immunosuppressive treatment, comprise ~3 million people in the UK. These individuals have suboptimal responses to vaccination and remain at an increased risk of severe COVID-19. ^{2,3} The QCOVID team and others have also identified additional disease groups who are increased risk of severe COVID-19, where immune dysfunction is recognised but is mechanistically poorly understood (e.g. renal disease, liver disease, diabetes, and Parkinson's disease).⁴ Even in healthy people, current COVID-19 vaccines give limited protection against SARS-CoV-2 infection, but rather protect against severe disease. Healthy people almost universally generate high titre serological responses to vaccines. By contrast, in many disease populations the response to vaccines is suboptimal, however this is heterogeneous, and the antibody response is difficult to predict. The precise correlates of protection against infection and severe disease remain poorly understood, but emerging data particularly in patient groups suggests that the serological response to vaccination is a critical determinant in COVID-19 clinical outcomes. Serological heterogeneity together with clinical phenotypes in disease groups gives an opportunity to define these correlates more precisely, and to identify populations who remain most susceptible to severe COVID-19 clinical outcomes.

Identifying individuals who continue to be at risk of severe COVID-19 despite vaccination, and who might benefit from additional treatment strategies remain challenging. This requires the clinical characterisation of multi-disease patient groups alongside vaccine response assessment using standardised immune assays and correlation with COVID-19 infection outcomes. Furthermore, assessment in real time is required as new Variant of Concern (VoC) emerge and the number of vaccines administered, and more recently vaccine type, continues to evolve over time.

To address this challenge, we will investigate whether SARS-CoV-2 antibody testing can better quantify an individual's risk and enable clinicians to provide targeted advice to those previously requested to shield and have been deemed Clinically Vulnerable.

2.1 Overall summary of Study

There will be two key workstreams to achieve the study aims. Firstly, a retrospective meta-analysis of existing data from clinical studies undertaken during the COVID-19 pandemic. These data have not been analysed in a comparative way to understand the breadth and diversity of clinical vulnerability, and results from this analysis may further inform on the CV groups that require prospective evaluation. Secondly, a prospective study that will recruit up to 3000 CV individuals, to understand how SARS-CoV-2 antibody tests, following COVID-19 vaccines, predicts COVID-19 risk.

Version: 2.0 26.11.2023 IRAS:325967

Sponsor: University of Birmingham

3.0 Retrospective meta-analysis (Lead: [name] / [name])

Aim: We will perform a meta-analysis of post-vaccination SARS-CoV-2 antibody concentrations in CV patient populations to discriminate SARS-CoV-2 infection risk and inform the clinical use of serological testing.

Objectives:

- 1) To investigate if a detectable SARS-CoV-2 antibody response (binary yes/no) post-vaccination predicts infection outcomes (rates and severity) across different CV groups.
- 2) To investigate if the post-vaccination antibody magnitude can predict infection across different CV groups.
- 3) To identify and refine CV patients to be included in the prospective study.

Methodology: Using existing combined UK cohorts of >15,000 immunosuppressed patients, a metaanalysis will be performed on published (and unpublished) data reporting linked vaccine immunogenicity and effectiveness outcomes. Studies to be included are shown in **TABLE 1**, with chief investigator approvals already obtained. This will include only anonymised patient data. Patient identifiable data will not be made available to the study team for the retrospective analysis.

The data will be pooled to maximise the statistical power for descriptive and comparative analysis. A minimum number of key characteristics will be collected in all studies (age, gender, primary disease type, treatment, vaccine number and type, anti-spike (S) IgG level and clinical outcome).

Different antibody tests have been used for these studies; to ensure this analysis is transferable across assays, the WHO International Standard will be used to compare platforms. Descriptive statistics will set out the geometric mean titres of IgG antibodies by age, gender, disease type and treatment, and compared with control cohorts within the included studies. Preliminary analysis of the association between antibody concentration and effectiveness will include post-vaccination (≥3rd dose) antibody status in immunosuppressed people-antibody status will be considered as a binary value (detectable versus absent). Clinical outcomes of interest will include infection, hospitalisation and death; first considered as a composite, and then individually, data allowing. The odds ratio of clinical outcome by antibody status will be reported both unadjusted and adjusted for key participant (or patient − terms used interchangeably) characteristics. We will also explore the relationship between antibody concentrations as a continuous variable and clinical outcomes, with estimation of discriminative cut points at concentration levels associated with inferior effectiveness. A repeat analysis will be performed on non-immunosuppressed vulnerable people within these cohorts. Those groups with inadequate response with respect to the clinical outcomes as determined by these analyses would be included in the prospective study.

Data sharing and transfer: We will request ethical approval to use existing data from other studies to achieve the aims of STRAVINSKY. This will enable the development of data transfer arrangements between the existing studies with the STRAVINSKY team. Before doing this the data transfer arrangements will ensure the correct ethical approvals are in place and patients have consented for their data to be used in future ethically approved studies. The data transferred will be at patient level but will be completely anonymised. Data will be stored on secure servers at all times and transferred using encrypted files.

TABLE 1. Examples of studies to be included in the retrospective meta-analysis

Study	Patient Cohort	Numbers of participants
OCTAVE	Rheumatology, Solid Organ	2,686
	Transplants, Renal, Liver, Stem	
	cell Transplant	
OCTAVE-DUO	Rheumatology, Solid Organ	804
	Transplants, Renal, Liver, Stem	
	cell Transplant, lymphoma,	
	antibody deficiency	
PROSECO	Immunodeficiency	592
COVAD	Immunodeficiency	562
CORONACANCER	Cancer	3,555
CLARITY	Inflammatory bowel disease	7,224
COVID-19 RENAL	Renal Transplant, Dialysis,	2,500
	Autoimmune, Renal disease	
PITCH	Health care workers (control)	800

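### The minimum data set for the retrospective pooling does not require sample-to-infection timing, follow-up time or prior infection, and the stated odds ratio is adjusted for participant characteristics but not for study or period

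*Protocol*

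**What the plan says.** Section 3.0 combines existing UK cohorts, described as "data reporting linked vaccine immunogenicity and effectiveness outcomes". Objective 1 is whether a detectable antibody response predicts infection outcomes, both rates and severity. Objective 2 asks the same of antibody magnitude for infection.

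On the data: "A minimum number of key characteristics will be collected in all studies", namely "age, gender, primary disease type, treatment, vaccine number and type, anti-spike (S) IgG level and clinical outcome". On combining the studies: "The data will be pooled to maximise the statistical power for descriptive and comparative analysis". On the level of data: "The data transferred will be at patient level but will be completely anonymised".

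The preliminary analysis uses "post-vaccination (≥3rd dose) antibody status in immunosuppressed people", taken as detectable or absent. Outcomes are infection, hospitalisation and death, first as a composite. "The odds ratio of clinical outcome by antibody status will be reported both unadjusted and adjusted for key participant" characteristics. Antibody concentration is also explored as a continuous variable, with estimation of discriminative cut points. On use of the result: "Those groups with inadequate response with respect to the clinical outcomes as determined by these analyses would be included in the prospective study".

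Section 3.0 gives no sampling window other than dose three or later, no start or end of the risk period, and no term for study or calendar period. Section 11.0 points to Appendix 3 for the statistical analysis plan, and Appendix 3 describes only the prospective study.

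**The concern.** Prediction requires the antibody sample to come before the infection, and a rate requires time at risk. The listed items supply neither. Infection itself can raise anti-spike antibody; section 9.1 says of the prospective assay that it detects antibody after infection and cannot tell it from vaccine antibody. A patient infected before sampling can therefore be antibody-detectable because of the infection and also be counted as an outcome. Adjustment for age, disease or treatment does not repair that.

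The second problem is confounding by study. If cohorts differ both in the share with detectable antibody and in the share infected (through background risk or length of follow-up), pooling patients creates or hides an association that exists in no single cohort.

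At stake are the retrospective odds ratios, the cut points, and any change to the eligible groups that rests on them.

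**Working it through.** **The plan's own figure.** The Table 1 cohorts without the health care worker controls sum to 2,686 + 804 + 592 + 562 + 3,555 + 7,224 + 2,500 = 17,923, which agrees with the stated figure of more than 15,000. Section 3.0 gives no event count, power or expected odds ratio to reproduce.

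**What the question needs against what is assured.**

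| Needed | In the section 3.0 minimum set | In the prospective part (Appendix 3) |
|---|---|---|
| Start of the risk period | Not listed | Infections from at least 14 days after vaccination |
| Time from vaccine to sample | Not listed | Adjustment required in the Visit 1 analysis |
| Prior infection | Not listed | Described at baseline |
| Time at risk | Not listed | Time-to-first-infection sensitivity analysis |
| Study or period in the model | Not stated | Not applicable to study (one cohort) |

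The prospective part asks much the same question and provides for the first four.

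**Crude pooled odds ratio with no within-study effect.** For study i let n be its size, d the proportion detectable and r the infection risk, with r the same in detectable and absent patients (within-study odds ratio 1). Then

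- detectable: infected = Σ n·d·r, uninfected = Σ n·d·(1−r)
- absent: infected = Σ n·(1−d)·r, uninfected = Σ n·(1−d)·(1−r)

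and the odds ratio is the ratio of the two odds. All values of d and r are assumptions.

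Two studies of 1,000 each:

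- d = 70%, r = 10% and d = 90%, r = 30%: infected 70 + 270 = 340 of 1,600 detectable, 30 + 30 = 60 of 400 absent. OR = (340/1,260)/(60/340) = 1.53.
- Risks swapped: 300 of 1,600 and 100 of 400. OR = (300/1,300)/(100/300) = 0.69.
- d = 60%, r = 5% and d = 95%, r = 30%: 315 of 1,550 and 35 of 450. OR = (315/1,235)/(35/415) = 3.02.

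Two of the Table 1 cohort sizes, 7,224 and 2,500:

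| Detectable, first vs second | Risk 10% vs 30% | Risk 20% vs 30% | Risk 30% vs 10% |
|---|---|---|---|
| 90% vs 80% | 0.78 | 0.91 | 1.21 |
| 95% vs 70% | 0.53 | 0.77 | 1.77 |
| 98% vs 60% | 0.41 | 0.69 | 2.52 |

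**Unequal follow-up alone.** Same sizes, 95% vs 70% detectable, one assumed rate of 2% per month in both, r = 1 − exp(−0.02·months). Follow-up of 3 vs 12 months gives risks of 5.8% and 21.3% and OR 0.51; 6 vs 12 months gives 0.70; 12 vs 3 months gives 1.82.

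The crude odds ratio is 1.00 whenever detectability or risk is equal across the studies, and the study-stratified odds ratio is 1.00 throughout by construction.

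**What adjustment for disease type would do.** Where a cohort holds one disease (inflammatory bowel disease in CLARITY), disease type stands in for study and removes much of this. It does not where a disease spans cohorts: Table 1 has renal and transplant patients in OCTAVE, OCTAVE-DUO and COVID-19 RENAL, and immunodeficiency in PROSECO, COVAD and (as antibody deficiency) OCTAVE-DUO. The remainder after adjustment cannot be computed from the documents, nor can the bias from infections before the sample.

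**The case against.** The strongest reply is that the list is a floor. Nothing forbids further fields, the data are at patient level, and the source studies link immunogenicity to outcomes, so dates may well come with them. The work is called a meta-analysis and uses control cohorts within the included studies, so study of origin is probably known. Model form is often left to an analysis plan, and a retrospective one may exist that is not shown. The binary analysis is labelled preliminary, and the retrospective work is a secondary objective.

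Most of this stands, and it rules out stronger readings. A reader might infer that no dates will be collected and that infections can never be placed after the sample; the text supports this only for the listed minimum. A reader might infer that the odds ratio is certain to mix antibody with epidemic wave; Table 1 gives no calendar dates, so differing periods are a possibility and not a documented fact. A reader might infer that the error passes into the prospective study; but Table 2 already lists 20 groups, section 5.1 says only that these may alter in the light of the retrospective results or other knowledge, and Appendix 3 defines low antibody from the lower 10th percentile of healthy controls, not from retrospective cut points.

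The objection does not remove the point. The minimum is all that is assured from every study, so it limits what can be analysed across all of them. Once data arrive fully anonymised, missing intervals cannot be linked back without a new transfer. No later analysis plan can use fields that were not requested.

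**Conclusion.** The point holds for the minimum data set and adjustment set as written. Followed as stated, they cannot show that infections came after the antibody sample, cannot give rates, and leave the pooled odds ratio open to bias from between-study differences in infection risk or follow-up. The bias can go either way and its size is unknown. The illustrative range of about 0.4 to 3.0 is for crude odds ratios, rests on assumed detectability, risks and follow-up, and overstates what would remain after adjustment for disease type.

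The consequence is confined to the retrospective estimates, the cut points, and any changes these prompt to the Table 2 groups. This is an inexpensive improvement that should be made; it does not undermine the prospective primary analysis.

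**What to change.** In section 3.0, add to the minimum data set:

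- study identifier;
- calendar month or quarter of the antibody sample;
- intervals in days from the sample to last dose, to infection or hospitalisation, and to end of follow-up;
- infection before the sample (yes/no).

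Intervals with a month or quarter, in place of full dates, fit the commitment to anonymised data.

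State that only infections after the sample count as outcomes. Estimate the association within study, by a study-stratified model or a two-stage meta-analysis, taking calendar period and follow-up time into account, and apply the same rule to the cut-point analysis.

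The cost is a few extra fields in the data request and some rewording of section 3.0. The drawback is that a study unable to supply the intervals would contribute descriptive data only, which reduces the number of patients in the comparative analysis.

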4.0 Prospective observational study (Lead [name]/[name])

4.1 Aim

To assess the predictive value of post SARS-CoV-2 vaccination serology measurements in CV individuals.

4.2 Objectives

Primary objectives:

a) To define and assess the predictive value of SARS-CoV-2 spike serology measurements for COVID-19 clinical outcomes (infection rates and disease severity) in CV people.

Secondary objectives:

- a) To evaluate the serological vaccine responses (magnitude and durability) of CV patients to bivalent or other vaccines given during the study period.
- b) To assess the functional activity of anti-spike IgG antibodies against new SARS-CoV-2 variants in CV patients during the study period.

Exploratory objectives:

- a) To evaluate alternate methods to predict COVID-19 infection/hospitalisation should antibody testing fail to predict relevant clinical outcomes (e.g. QCOVID4 score and T cell responses).
- b) To understand whether the serology vaccine response, in those with suboptimal responses to primary course, can be further enhanced with increasing doses of vaccination. \Box
- c) To assess T-cell response to emerging VoC in CV individuals.
- d) To determine the correlation between antibody and T-cell responses

Version: 2.0 26.11.2023 IRAS:325967

5.0 Study population and eligibility criteria

5.1 Patient selection

Participants in this study will have an underlying disorder which has identified them as being clinically vulnerable. The disease and treatment groups eligible for participation (**TABLE 2, page 13**) in STRAVINSKY may alter throughout the study depending on the results from the retrospective analysis or other new knowledge/discussions such as the report from the Independent Advisory Group for COVID-19 medicines.⁵

TABLE 2. Groups eligible for participation

Group	Disease related groups (n=120-140 per group)				
1	Chronic lymphoproliferative disorders (footnote 1)				
2	Plasma cell disorders (footnote 2)				
3	Myelodysplastic syndrome (MDS) or (myeloproliferative neoplasms MPN) (footnote 3)				
4	Sickle cell disease, thalassaemia, or rare inherited anaemias				
5	Active malignancy diagnosed within 2 years of study consent (excluding non-melanoma skin cancer, non-invasive bladder cancer and localized squamous cell carcinoma of cervix)				
	(Note: participants who have received radiotherapy or systemic anti-cancer treatment within the last 26 weeks should be included in groups 18 and 19 first).				
6	Down's syndrome and learning disability				
7	Neurological diseases (Parkinson's and mult	iple sclerosis) (footnote 4)			
8	HIV				
9	Common variable immunodeficiency an prophylactic antibiotics and/or immunoglob	d secondary immunodeficiency (requiring ulin)			
10	Cirrhosis (footnote 5)				
11	Chronic respiratory conditions (footnote 6)				
12	Chronic kidney disease (CKD) stage 4-5 (foot	note 7)			
13	Diabetes mellitus (Type 1 and 2)				
14	Cardiac failure				
	Treatment-related group	Timing			
	(n=120-140 per group)				
15	Previous recipients of a solid organ transplant (SOT)	At any time			
16	Recipient of a haematopoietic stem cell transplant (HSCT)	Within 52 weeks at time of study consent			
17	Recipient of B-cell depleting treatment (APPENDIX 1 for details)	Within 52 weeks at time of study consent			
18	Recipient of systemic anti-cancer therapy e.g. chemotherapy or immunotherapy and others (APPENDIX 1 for details)	Ongoing or within last 26 weeks at time of study consent			
19	Recipient of radiotherapy	Ongoing or within last 26 weeks at time of study consent			
20	Autoimmune disease on systemic immunosuppressive* medication (APPENDIX 1 for details)	Ongoing or within last 26 weeks at time of study consent			

If a participant belongs to more than 1 disease/treatment group, allocation will follow the following prioritisation:

Does the patient fit into any of the treatment-related groups?

Yes —> allocation to Treatment-related group. Patients should be preferentially allocated to the first treatment-related group that can be applied to them in the list above from rows 15 to 20 above.

No -> allocation to disease-related group that is considered by the local clinical investigator to be the MAIN disease. Patients should be preferentially allocated to the first disease-related group that can be applied to them in the list above from rows 1-14 above.

Footnotes:

- 1. Any chronic/indolent/low-grade B or T-cell lymphoproliferative disorder e.g. follicular lymphoma, chronic lymphocytic leukaemia, lymphoplasmacytic lymphoma etc.
- 2. e.g. myeloma, plasma cell leukaemia and AL amyloidosis and excluding monoclonal gammopathy of undetermined significance (MGUS).
- 3. Includes myelodysplastic syndrome, myeloproliferative neoplasms, myelofibrosis and chronic myelomonocytic leukaemia.
- 4. Any rare neurological and severe complex neurodisability e.g. multiple sclerosis, motor neurone disease, myasthenia gravis, Huntingdon's disease, and also Parkinson's disease.
- 5. Cirrhosis Child-Pugh class A, B and C.
- 6. Chronic obstructive pulmonary disease, Interstitial Lung disease, Pulmonary hypertension
- 7. eGFR less than 30 ml/min/1.73m²

